## 8.2.1 Participant ADAb classification

Study participants from the SS will be classified based on their baseline and treatment-emergent ADAb status (Table 8–2). Classification will be done separately for two time periods of interest: (1) using the study participants' data for the entire study treatment period and (2) using the study participants' data up to and including Week 24 (to facilitate comparison with adult RA data from study RA0138 in the Updated Week 24 Interim Analysis). Baseline ADAb values are defined as the latest (not missing, not inconclusive) measurements up to and including the date of administration of first CZP treatment.

Table 8–2: ADAb status classification at participant level

	1.	Baseline ADAb negative and treatment-emergent ADAb negative	Study participants who were negative at Baseline and negative at all sampling points post treatment until the time point of interest
71	nerit c	Bulling	Note: study participants with Baseline samples missing and negative ADAb status at all sampling points post treatment are included in this category because participants who are pre ADAb positive are expected to have ADAb positive samples post-dosing.

Table 8-2: ADAb status classification at participant level

2.	Baseline ADAb negative and treatment-emergent induced ADAb positive	Study participants who were negative at Baseline and positive at any sampling point post treatment until the timepoint of interest. This group also included study participants who had a missing Baseline sample with 1 or more positive post treatment samples.
3.	Baseline ADAb positive and treatment-emergent reduced ADAb negative	Study participants who were positive at Baseline and negative at all sampling points post treatment until the timepoint of interest.
4.	Baseline ADAb positive and treatment-emergent unaffected ADAb positive	Study participants who were positive at Baseline and were positive at any sampling point post treatment until the timepoint of interest with all titer values of the same magnitude as Baseline (i.e., less than or equal to a predefined fold increase from the Baseline value of 2.10 which is defined with the validation of the assay).
5.	Baseline ADAb positive and treatment-emergent boosted ADAb positive	Study participants who were positive at Baseline and were positive at any sampling point post treatment until the timepoint of interest with any increased titer values compared to Baseline (greater than a predefined fold increase of 2.10 from Baseline value which is defined within the validation of the assay).
6.	ADAb inconclusive	Study participants who were positive at Baseline and some post-treatment samples until the timepoint of interest were missing or inconclusive, while other post-treatment samples until the timepoint of interest were negative.  Note: study participants who were positive at Baseline and all post-treatment samples up to the timepoint of interest were missing or inconclusive are also included in this category.
7.	Treatment emergent ADAb positive	Study participants that were classified as 2 or 5.
8.	Baseline treatment ADAb positive	Study participants who are positive ADAb at baseline, so those classified as 3, 4, 5 or 6.
9.	Missing USE	Study participants who were negative at Baseline or missing their Baseline assessment, were not positive at any post-Baseline visit, and have at least one missing/or inconclusive post-treatment scheduled assessment (until the timepoint of interest).
10	ADAb positive	Study participants who have a positive ADAb sample status at any timepoint (either Baseline or post dose).

Unscheduled visits including early discontinuation visits (ED) or Final visits with missing results are disregarded. Thus, study participants who had missing ADAb measurements at ED but were ADAb negative at all other post-treatment visits will be classified in category 1

Confidential Page 49 of 252

above. Study participants who were negative at Baseline or missing their Baseline assessment and whose only post-treatment ADAb assessment was at ED and was missing will be classified in category 9 above. Study participants who were positive at Baseline and whose only post-treatment assessment was at ED and was missing will be classified in category 6 above. Only positive data at unscheduled visits will be used for classification.

Table 8-3:	Aid to Programming	ADAb partici	pant status category

ADAb Participant Status Category	Post-Treatment ADAb Sample Status a		ample Status a
Baseline ADAb Sample Status	Any Positive	All Scheduled Negative	Some/All Scheduled Missing b
Missing	2	1	9
Negative	2	1 , 1	9
Positive	4 or 5 c	3	6

<sup>a Unscheduled (including withdrawal visits) with missing data disregarded. Missing data at other (scheduled) visits considered.

Post-treatment ADAb sample status categories are mutually exclusive and applied left to right. Thus study participants with both positive and missing post-treatment ADAb samples are considered in the "Any Positive" category.

Time point of interest is the entire treatment period including SFU and the treatment period up to Week 24.

## 8.2.2 ADAb Titer Classification

To further evaluate the impact of ADAb on PK, efficacy and safety, grouped ADAb titer categories will be defined based on ADAb quartiles (see Section 4.7) observed in the study. Quartiles will be calculated separately for the entire treatment period, and then for the period up to and including Week 24, using each study participant's highest post-treatment ADAb titer (ADAb negative participants will be deemed to have zero titer levels for calculation purposes). If all post-baseline scheduled visit results are Negative, then the study participant will be assigned to the lowest titer classification (lowest quartile); unscheduled visits with missing results are disregarded. If a study participant doesn't have any positive results at post-baseline scheduled visits and any of the results at scheduled visits are deemed missing or inconclusive, then the study participant will be assigned to "Missing".

If interpretation of the grouped titer summaries is inconclusive or results from other studies suggest other groupings, additional post-hoc analyses may be conducted to further investigate.

Immunogenicity will be assessed through summary tables and figures and listing of individual results by study participant on the SS. Summaries will be by CZP dose (Reduced

<sup>b And no positive ADAb samples post-treatment (including positive in either scheduled or unscheduled).

<sup>c Highest ADAb titer used to determine category.

CZP Dose, Original CZP Dose) and each of Baseline weight group, Baseline age group, and concomitant MTX use, unless specified otherwise.

- Number and percentage of study participants with positive, negative, inconclusive or missing ADAb sample status (Table 8–1) will be summarized at each visit and overall and by dose (Original CZP dose, Reduced CZP Dose).

  The number and percentage of study participants in a categories (overall and up to Week 24 summarized. Percentage of the categories (overall and up to Week 24 summarized. Percentage of the categories (overall and up to Week 24 summarized. Percentage of the categories (overall and up to Week 24 summarized. Percentage of the categories (overall and up to Week 24 summarized. Percentage of the categories (overall and up to Week 24 summarized. Percentage of the categories (overall and up to Week 24 summarized. Percentage of the categories (overall and up to Week 24 summarized. Percentage of the categories (overall and up to Week 24 summarized. Percentage of the categories (overall and up to Week 24 summarized. Percentage of the categories (overall and up to Week 24 summarized. Percentage of the categories (overall and up to Week 24 summarized. Percentage of the categories (overall and up to Week 24 summarized. Percentage of the categories (overall and up to Week 24 summarized. Percentage of the categories (overall and up to Week 24 summarized. Percentage of the categories (overall and up to Week 24 summarized. Percentage of the categories (overall and up to Week 24 summarized. Percentage of the categories (overall and up to Week 24 summarized. Percentage of the categories (overall and up to Week 24 summarized. Percentage of the categories (overall and up to Week 24 summarized. Percentage of the categories (overall and up to Week 24 summarized. Percentage of the categories (overall and up to Week 24 summarized. Percentage of the categories (overall and up to Week 24 summarized. Percentage of the categories (overall and up to Week 24 summarized.)
- been classified as per Table 8–2, so including missing /inconclusive participants.

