## 8.2 Anti-CZP antibodies

Immunogenicity will be assessed through listing of individual results by study participant and summary tables and graphs for data generated with the ECLIA method only for the SS. Immunogenicity data will be related to PK (using the PK-PP set), efficacy (using the FAS) and safety (using the SS). All data including those results at the Final Visit will be used for analyses for the entire study.

Anti-drug antibodies will be assessed by a three-tiered approach: screening (positive or negative screen), confirmatory (positive or negative immuno-depletion) and titer assays, using ECLIA methods. Cut points will be determined during assay validation and used by the bioanalytical laboratory to determine the status of ADAb in the test samples as described in Table 8–1.

Table 8-1: ADAb status at sample level

	ADAb positive	Sample values that are 'positive screen' and 'positive immuno-			
	(ADAb+)	depletion.'			
	100 V				
	ADAb negative	Sample values that are either 'negative screen' or 'positive screen' and			
	(ADAb-)	'negative immuno-depletion' if corresponding drug levels are equal or			
	, Co.	below the validated drug tolerance limit of the assay allowing detection			
	o'll'	of 100 ng/ml ADAb positive control or limit dictated by the ADAb assay			
9		and project needs (e.g. 250 ng/ml positive control).			
	ADAb negative	Sample values that are either 'negative screen' or 'positive screen' a 'negative immuno-depletion' if corresponding drug levels are equal below the validated drug tolerance limit of the assay allowing detection of 100 ng/ml ADAb positive control or limit dictated by the ADAb assay			

Table 8–1: ADAb status at sample level

ADAb inconclusive	Sample values that are either 'negative screen' or 'positive screen' and 'negative immuno-depletion' but with corresponding drug levels above the validated drug tolerance limit of the assay allowing detection of 100 ng/ml ADAb positive control or limit dictated by the ADAb assay and project needs (e.g. 250 ng/ml positive control).
Missing	Samples that were not collected per schedule or that could not be tested for ADAb status due to inadequate sample volume, mishandling, or errors in sample collection, processing, storage, etc.

Confirmed positive samples will be titrated and the titer will be reported including the minimum required dilution (MRD) of the assay.

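### SAP Section 8.2.2 conflicts with itself and with 8.2.1: read literally, a participant whose only positive ADAb is at an unscheduled visit goes to the lowest titer quartile or to Missing despite a measured titer

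*SAP*

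**What the plan says.** Section 8.2.2 first defines the quartiles "using each study participant's highest post-treatment ADAb titer", separately for the entire treatment period and up to Week 24, and gives a zero titer only to ADAb negative participants. Two assignment sentences follow.

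- Lowest class: "If all post-baseline scheduled visit results are Negative, then the study participant will be assigned to the lowest titer classification (lowest quartile". The same sentence goes on to say that "unscheduled visits with missing results are disregarded".
- Missing class: "If a study participant doesn't have any positive results at post-baseline scheduled visits and any of the results at scheduled visits are deemed missing or" (the sentence then names an inconclusive result as the alternative). Such a participant goes to Missing.

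Section 8.2.1, which sets the participant-level ADAb status, takes in positives from outside the schedule: "Only positive data at unscheduled visits will be used for classification". Footnote b to Table 8-3 allows the missing/inconclusive column only under the condition "And no positive ADAb samples post-treatment (including positive in either scheduled or unscheduled", and the notes to that table apply the Any Positive column first.

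On which visits are unscheduled, 8.2.1 says: "Unscheduled visits including early discontinuation visits (ED) or Final visits with missing results are disregarded". Footnote a to Table 8-3 places withdrawal visits among the unscheduled ones and does not name the Final Visit. Section 8.2 adds: "All data including those results at the Final Visit will be used for analyses for the entire study".

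**The concern.** The same participant can be ADAb positive in one table and sit with the zero-titer or unclassifiable participants in the next. Nothing in 8.2.2 tells a programmer which of its rules prevails, so two people working from this text could produce different classes.

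Titer class is a grouping variable for disposition (5.1), demographics (6.1), plasma concentrations (8.1, 8.3), TEAEs (9.2) and PedACR response (10.2, 10.3.1). If titer is related to exposure, response or safety, placing participants with a real titer in the lowest class, or dropping them into Missing, would blur that relation.

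**Working it through.** No sample size, power or event figure is involved and the SAP states no figure to reproduce. The check applies the rules side by side to a participant whose only post-treatment positive, with measured titer T > 0, is at an unscheduled visit.

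| | Case 1 | Case 2 |
|---|---|---|
| Scheduled post-treatment results | all negative | none positive, at least one missing or inconclusive |
| Status (8.2.1), Baseline negative or missing | category 2 | category 2 |
| Status (8.2.1), Baseline positive | category 4 or 5, by the 2.10-fold rule | category 4 or 5, by the 2.10-fold rule |
| Titer class, highest-titer rule (8.2.2) | set by T | set by T |
| Titer class, assignment sentences (8.2.2) | lowest quartile | Missing |

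The last two rows come from the same section and disagree. The last row also disagrees with 8.2.1. The two Missing definitions show why: category 9 in Table 8-2 requires no positive at any post-Baseline visit, whereas Missing in 8.2.2 requires only no positive at scheduled visits.

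**When the literal placement is wrong.** Section 4.7 defines the lowest class as titers from 0 up to Quartile 1.

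- Case 1 is misplaced when T > Quartile 1. If more than a quarter of participants have zero titer (an assumption; the SAP gives no rate), Quartile 1 = 0 and every T > 0 is misplaced. If fewer than a quarter do, Quartile 1 > 0 and a T at or below it belongs in the lowest class anyway.
- Case 2 is misplaced for any measured T, because a titer exists and the class is Missing.

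**Which visits are involved.**

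- Early discontinuation: Section 3.2.1 moves ED/EOT data to the next scheduled visit unless something else is specified. For ADAb something else is specified, since 8.2.1 and footnote a to Table 8-3 treat ED as unscheduled.
- Final Visit: open. The 8.2.1 sentence can list it as one kind of unscheduled visit or beside them. Table 2-2 and the sampling times in 8.1 include it as planned. If it is scheduled, neither assignment condition is met by a Final Visit positive and T sets the class.

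**Can Case 2 occur at the Final Visit, if that visit is unscheduled?** Section 9.1 equates 70 days with 5 half-lives, so one half-life is 70 / 5 = 14 days. The Final Visit is 12 weeks = 84 days after the last dose (3.2.4), which is 84 / 14 = 6 half-lives and leaves 0.5^6 = 1.6% of the drug. Under Table 8-1, a screen-negative or unconfirmed sample is inconclusive when drug is above the tolerance limit. Inconclusive samples on treatment followed by a positive after washout are therefore possible. How often this happens cannot be derived from the SAP.

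**The case against.** A reader might infer that the titer classification is settled as scheduled visits only. The SAP does not support that. The highest-titer rule has no such limit, zero is reserved for ADAb negative participants, and the lowest-class sentence disregards unscheduled visits only when their results are missing, which suggests that unscheduled positives were meant to count. On that reading the two assignment sentences were meant for participants with no positive result at all. This stands as evidence of intent, but no sentence in 8.2.2 says so, and the Missing sentence as written says otherwise.

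A reader might also infer that every participant with a late-only positive is misplaced, or that late visits are where antibodies are most likely to appear. The first fails when T is at or below Quartile 1 in Case 1, and when the Final Visit counts as scheduled. The second goes further than Table 8-1, which shows only that high drug levels can make a sample inconclusive.

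Reach is limited too. A Final Visit positive would normally leave the Week 24 class unchanged, and the adult comparison at Weeks 12 and 24 is complete and will not be rerun (12.1). Section 8.1 says that plasma concentration samples were not collected after Protocol Amendment 8 for earlier enrollees; whether ADAb sampling also stopped is not stated in the current text. The study is descriptive, with no hypothesis tests (3.1, 4.5), and tables by ADAb status follow 8.2.1 and are unaffected.

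**Conclusion.** The point holds as an internal conflict. The assignment sentences of 8.2.2, applied as written, contradict that section's own highest-titer rule and give a result at odds with 8.2.1 for any participant whose only positive is unscheduled. ED positives are clearly within reach, because the ADAb text treats ED as unscheduled. Final Visit positives are within reach only if that visit is also unscheduled, and then normally only for the entire-period class.

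The size cannot be stated. It runs from zero up to the number of participants whose only positive with a measured titer is at such a visit, and the SAP gives no count or rate. Any percentage would only repeat the share assumed. The conflict should be corrected because it affects a subgroup used across PK, efficacy and safety tables, but no formal inference depends on it.

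**What to change.** In Section 8.2.2:

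1. Add to both assignment sentences the condition *and no positive result at any unscheduled, ED or Final visit in the period*.
2. State that the highest titer from any post-treatment visit in the period sets the class.
3. State whether ED and Final visits count as scheduled for ADAb, and use the same definition in 8.2.1 and in the footnotes to Table 8-3.

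The cost is a few sentences of SAP text and a matching check of the derivation program. No new data are needed, and 8.2.2 then agrees with 8.2.1.

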## Prevalence and incidence:

- Prevalence of Baseline ADAb positivity: number and percentage of study participants that have Baseline positive ADAb sample status, with the denominator for percentages defined as all participants having an evaluable (not missing, not inconclusive) Baseline ADAb sample.
- Incidence of treatment-emergent ADAb positivity: number and percentage of study participants with either treatment boosted ADAb or treatment induced ADAb, with the denominator for percentages all participants except those categorized as inconclusive or missing (overall for the entire treatment period and then up to and including Week 24).

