## 8.2.3 Time to first occurrence of treatment-emergent ADAb positivity

Study participants will be considered to have an event at the first ADAb sampling time point with ADAb positive status in the entire treatment period if the participant is Baseline ADAb negative or first ADAb sampling time point with fold difference increase from Baseline > 2.1 if participant is Baseline ADAb positive. Study participants who are never treatmentemergent ADAb positive will be censored at the date of the last evaluable (not missing, not inconclusive) ADAb sample or on date of first CZP if no evaluable post-treatment ADAb samples. In case of Baseline ADAb positivity present in more than 10% of the study participants, the table will be produced separately for ADAb participant category 2 (induced) and 5 (boosted).

- Summary tables based on Kaplan-Meier (KM) estimates will be produced.
- Kaplan-Meier plots of time to first treatment-emergent ADAb positivity will also be produced separately for the CZP doses (Original CZP dose, Reduced CZP dose). All available data timepoints will be included.

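### Treatment-emergent ADAb incidence demands complete, conclusive sampling of negatives but not of positives, so it reads too high if samples are lost independently of antibody status

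*SAP*

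**What the plan says.** Section 8.2.2 (Prevalence and incidence) counts boosted or induced participants in the numerator. In Table 8-2 the treatment-emergent positive group is: "Study participants that were classified as 2 or 5". The stated "denominator for percentages all participants except those categorized as inconclusive or missing" leaves categories 1 to 5 and removes categories 6 and 9. The figure is produced for the entire treatment period and up to Week 24.

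The two removed categories are defined in Table 8-2:
- Category 9 covers baseline-negative or baseline-missing participants who "were not positive at any post-Baseline visit, and have at least one missing/or inconclusive post-treatment scheduled assessment".
- Category 6 covers baseline-positive participants for whom "some post-treatment samples until the timepoint of interest were missing or inconclusive, while other post-treatment samples until the timepoint of interest were negative", or whose post-treatment samples were all missing or inconclusive.

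Positives get the opposite treatment in the notes to Table 8-3: "Thus study participants with both positive and missing post-treatment ADAb samples are considered in the" any-positive column. A missing result at an unscheduled, early-discontinuation or Final visit is disregarded and does not by itself move a participant to category 9.

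At sample level, Table 8-1 counts as missing a sample that "could not be tested for ADAb status due to inadequate sample volume". It counts as inconclusive a negative result obtained with drug above the assay's tolerance limit. Sections 2 and 2.3 make re-assay of archived samples depend on remaining volume.

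Three neighbouring outputs treat gaps differently. The category table uses all classified participants. The baseline prevalence uses participants with an evaluable baseline sample. Section 8.2.3 has never-positive participants "censored at the date of the last evaluable (not missing, not inconclusive) ADAb sample".

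**The concern.** Completeness is required for one outcome and not for the other. To stay in the denominator as a negative, a participant needs every scheduled sample present and conclusive. To stay in as a positive, one sample is enough. Sample loss therefore removes mostly negatives, and the rate rises without any change in immunogenicity.

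Immunogenicity is part of the primary objective (Section 2.1.1), and this is the only statistic that the SAP labels as incidence of treatment-emergent positivity. The distortion may also differ between dose groups. The Reduced Dose group was enrolled before Protocol Amendment 9 and depends on archived samples with enough volume left. The Original Dose group includes 30 later participants assayed directly by ECLIA. Section 3.1 also cuts each group's data at the first dose change, so the number of scheduled samples can differ. A difference in incidence between doses could then partly reflect sample availability.

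The same asymmetry sits in the titer classification of Section 8.2.2. A participant with no positive and one missing or inconclusive scheduled result is assigned to the Missing titer class, which is then used in safety and efficacy subgroups.

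**Working it through.** The SAP states no ADAb incidence and no sample-loss rate, so there is no figure to reproduce. The check asks what the rule returns when the truth is known.

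**Inputs**
- K, scheduled post-baseline samples: 6 to Week 24 (Weeks 1, 4, 12, 16, 17, 24) and 9 to Week 48 (adding 32, 40, 48). These come from the concentration schedule in Section 8.1. The current text gives no separate ADAb schedule, so the same one is assumed.
- π, true incidence among baseline-negative participants: assumed 40%.
- m, chance that a scheduled sample is missing or inconclusive: assumed 2%, 5% or 10%, independent of antibody status and of other samples.
- Positivity persists once it appears, with onset equally likely at each sample. A true positive then has j = 1 to K positive samples.

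**Formula**

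Retained positives: P = π × mean over j of (1 − m^j).

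Retained negatives: N = (1 − π) × (1 − m)^K.

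Reported incidence = P / (P + N).

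Because 1 − m^j ≥ 1 − m ≥ (1 − m)^K, the reported value is never below π. It is above π whenever K ≥ 2, m > 0 and 0 < π < 1.

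**Example, K = 6, m = 5%**

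P = 0.4 × 0.9912 = 0.3965. N = 0.6 × 0.95^6 = 0.6 × 0.7351 = 0.4411. Reported = 0.3965 / 0.8376 = 47.3%. About 16.2% of participants are dropped: 0.6 − 0.4411 = 15.9 points are true negatives and 0.4 − 0.3965 = 0.35 points are true positives.

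| True 40% | m = 2% | m = 5% | m = 10% |
|---|---|---|---|
| Reported, K = 6 | 42.9% | 47.3% | 55.2% |
| Share dropped, K = 6 | 7.0% | 16.2% | 28.9% |
| Reported, K = 9 | 44.4% | 51.3% | 63.0% |
| At-least-one-evaluable denominator, K = 6 | 39.9% | 39.6% | 39.3% |

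In a simulation with 193 participants and K = 6, Kaplan-Meier returned 40% at all three loss rates.

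**Clustered losses, m = 10%**

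Let losses correlate within participants (beta-binomial, all else unchanged; the correlation is an assumption).
- Correlation 0.3: the chance that all 6 samples are evaluable is 0.7062, against 0.9^6 = 0.5314 under independence. P = 0.4 × 0.9699 = 0.3879, N = 0.6 × 0.7062 = 0.4237, reported 47.8%. With K = 9 it is 0.3915 / (0.3915 + 0.3925) = 49.9%.
- Correlation 0.5: 0.3821 / (0.3821 + 0.4659) = 45.1% with K = 6, and 46.2% with K = 9.

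The bias stays but shrinks, and its growth with K nearly disappears.

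**Break-even for masked positives**

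Take an illustrative 163 + 30 = 193 participants, with 80 treatment-emergent positive, 40 dropped and 73 complete negatives. The rule gives 80/153 = 52.3%. Counting the dropped as all negative gives 80/193 = 41.5%, and as all positive 120/193 = 62.2%. The rule overstates unless at least 52.3% of the dropped participants, about 21 of 40, are truly positive.

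**The case against.** The strongest reply is that an inconclusive sample is not a negative one. Table 8-1 reserves that status for results that cannot be trusted because of drug in the sample. Leaving out people whose status cannot be determined is a defensible choice, and heavy masking could cancel or reverse the bias. This stands, and it is a reason to show bounds. It does not justify treating positives and negatives by different completeness rules.

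A reader might infer that the rate is inflated by construction because missingness deletes negatives only. The documents do not support that. A true positive whose positive samples are lost or masked also lands in category 9 or 6. If a participant's samples are all lost together, positives and negatives drop out alike and no bias follows. Only against the same numerator over all classified participants is the excess pure arithmetic.

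A reader might also treat this as the trial's headline rate. Section 2.2.1.1 names antibody levels at Weeks 16 and 48 as the primary immunological variable, and no hypothesis is tested. Nor does the SAP say that archived samples have more gaps than fresh ones, only that re-assay depends on volume. Much larger distortions from many years of samples cannot be applied across the board, because the dose groups stop at the first dose change.

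Finally, the category table, the by-visit status percentages and the Kaplan-Meier output let a careful reader see the gap. That is true, but the SAP does not say why the figures differ or which to rely on.

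**Conclusion.** The asymmetry is in the text and needs no assumption. The direction, upward, holds when samples are lost independently of antibody status. The size cannot be obtained from the SAP. For a true 40% to Week 24 it is roughly 3 to 15 percentage points at 2% to 10% independent loss per sample, assuming the ADAb schedule equals the concentration schedule. It falls to 5 to 8 points at 10% loss if losses correlate at 0.5 to 0.3 within participants. It could vanish or reverse if drug hides many positives in inconclusive samples. Disregarding missing early-discontinuation, Final and unscheduled results limits the exclusions somewhat. A difference in bias between dose groups is possible but not shown.

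The calculation covers baseline-negative participants. Baseline positives with an unaffected titer (category 4) stay in the denominator without entering the numerator. The rule should be changed before the final analysis.

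**What to change.** In Section 8.2.2, compute treatment-emergent incidence over participants with at least one evaluable post-baseline ECLIA sample, classed on their evaluable samples. Reserve missing/inconclusive for those with none. Then:
- report the Kaplan-Meier cumulative incidence, already planned in Section 8.2.3, at Weeks 24 and 48 beside it;
- add two bounds, counting the participants now dropped as all negative and as all positive;
- keep the current complete-sampling rule as a sensitivity table, for continuity with the Updated Week 24 Interim Analysis;
- apply the same rule to the Missing titer class.

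The cost is SAP wording, one changed derivation and a few table rows. The downside is that a negative status resting on fewer samples can slightly understate incidence (39.3% to 39.9% for a true 40% in the table above, and more if drug masks positives). The Kaplan-Meier estimate and the bounds make that visible.
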